Secondary Hypothesis: We hypothesize that the TV generated via PLV in the immediate neonatal transition phase will be highly variable.

PHASE II:

Primary Hypothesis: We hypothesize that real time PiP adjustments are feasible when utilizing a T-Piece resuscitator to provide VTV for goal TV of 4-6ml/kg that can be seamlessly transitioned in the NICU.

Secondary Hypothesis:

- i. We hypothesize that infants receiving VTV will require lower PiP, will have lower oxygen needs with improved long term pulmonary morbidities
- ii. We hypothesize that VTV will have lower complication rates as compared to PLV.

SPECIFIC AIMS:

PHASE I:

Specific Aim #1: To assess feasibility of measuring TV in the DR for preterm infants <32 weeks with need for invasive positive pressure ventilation via endotracheal tube (ETT).

Objectives:

Date 10/15/2018
Protocol Version-I

- To assess the % infants with all equipment ready(including NM3 monitor and flow sensor) in DR to measure TV
- To assess the % infants where TV was measured within 60 seconds of ETT placement and positive pressure ventilation initiation.

Specific Aim #2: To assess variability in delivered TV in the DR with PLV for preterm infants <32 weeks with need for invasive positive pressure ventilation via ETT

Objectives:

- To assess the % infants with tidal within goal of 4-6ml/kg via routine PLV
- To assess the % infants with under or over ventilation using routine PLV
- To assess changes in TV with administration of surfactant with the same pressures

PHASE II:

Specific Aim #1: To assess feasibility of providing VTV, by quickly adjusting the peak inspiratory pressures (PiP) provided via the T-Piece resuscitator based on real time TV measurements.

Objectives:

- To assess the recruitment rates and successful enrollment into the study
- To assess the % of infants with measurable TV and successful adjustment of PiP to reach goal TV
- To assess the % of infants who fail VTV and need to be switched to conventional PLV

Specific Aims #2: To compare the pulmonary mechanics and physiology during VTV, respiratory support requirements

Objectives:

- To compare TV delivered during PLV versus VTV.
- To compare FiO2 requirement during PLV versus VTV
- Evaluate PiP, mean airway pressures (Paw), peak end expiratory pressures (PEEP) and oxygen requirement during the first 48 hours between the two study arms.
- Evaluate differences in blood gas results (pH, PCO2 levels).

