PHASE I: No specific withdrawal/termination criteria will be required as this is an observational study to assess feasibility of measuring tidal volume in the DR. Infant will continue to receive routine care as recommended by NRP, even if TV measurements are unsuccessful.

PHASE II: Control Arm: No specific withdrawal/termination criteria will be required, as these infant will continue to receive routine care per NRP recommendations without any study related intervention.

Intervention Arm: If TV cannot be measured or VTV cannot be provided within 60 seconds of initiating PPV via the ETT, the infant will be automatically switched to receiving routine care as recommended by the NRP.

INFORMED CONSENT PROCESS AND TIMING

Who: Parent.

When: "Deferred consent" is being requested after the birth of the child. The study process starts as soon as the baby is born and requires intubation as determined by the clinical team providing resuscitation. We will obtain a deferred consent from the parents only if the baby requires intubation in the delivery room and the TV measurements were obtained. We will approach the parents to use the data that was collected in the delivery room.

Rationale for deferred consent: *In an ideal situation, the consent should be obtained prior to study intervention. However, since the study intervention starts within few seconds to minutes of the baby's birth and it is not*

possible to determine which baby will need intubation in the delivery room, it would be unrealistic to have the opportunity to obtain informed consent we will aim for "deferred consent" process. As this study only present minimal risk to the infants and the device being used is an FDA approved device for use in neonates, a deferred consent is being requested for from the IRB.

How much time to decide: Since study related interventions has already occurred and we are asking parents to give consent for using this information as well as review of electronic medical records parents will have adequate time to make this decision free of any coercion to participate in the study.

Person authorized to obtaining consent: All investigators, program coordinator associated with the study.

SUBJECT FEES: None

REIMBURSEMENT/RENUMERATION FOR PARTICIPTION: None

RISK BENEFIT ASSESSMENT

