Providing VTV to the VLBW infants is a standard of care practice upon admission to the NICU, with this study we seek to provide more physiologic VTV to the infant immediately after birth without any delay.

Phase I: No risk and no benefit directly to the patient, as this is the observational phase of the study. Information obtained from this phase study may potentially be beneficial by supporting the need for future studies in preterm infants with need for invasive respiratory support.

Phase II: Infants in intervention arm will receive the same routine care with additional information about the TV being delivered to the study infants. The provider's ability to adjust the PiP to provide goal TV may be potentially beneficial for the study infants, as in current DR practice the delivered tidal volume is unknown and infant may be receiving TV out of the set goal range. Infants in the control arm will not have any direct risk or benefit. The only concern would be adding less than 1ml of dead space with the flow sensor, which may or may not be of any clinical significance at all.

UNANTICIPATED PROBLEMS AND SERIOUS ADVERSE EVENT REPORTING

Unanticipated problems and serious adverse events to the subjects related to the study will be reported to the IRB within 48 hours of the occurrence.

RANDOMIZATION

Phase I: No randomization. All infants will receive pressure regulated breaths, 40-60 breaths/min, PiP of 20-24cm of H₂O as recommended by 2017 Neonatal Resuscitation Program (NRP) guidelines. Providers will be blinded from the measured TV during the resuscitation.

Phase II: All infants born <32 weeks will be randomized to one of the study group. Randomization will be via sealed envelope, opened in DR after the decision to intubate is made, with a 1:1 randomization ratio. To keep the gestational age in the two study arm relatively similar, as we are proposing only a small sample size for this current study, randomization will be stratified by gestation age group (Randomization subgroup I: <28 weeks and subgroup II: 28-32 weeks). Infants in both the arms will have a flow sensor at the ETT connected to Respironics NM3 monitor (Philips Healthcare, Eindhoven, Netherlands), to measure breath to breath TV.

INTERVENTION

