Phase II: We will enroll a total of 30 patients (15 per study group). The sample size was selected to insure sufficient number of patients to estimate variability and effect sizes^{xxi} and to estimate recruitment rates. For example, with 30 patients, the width of the 95% confidence will be about 55% as wide as the standard deviation. This estimate will help develop sample size estimates for future studies.

DATA COLLECTION AND STORAGE

Study data will be collected and managed using a secure, web-based, password protected RedCap (Research Electronic Data Capture) data base^{xxii}. Baseline demographic maternal and infant characteristics, TV, PiP, mean airway pressure, PEEP, FiO₂, resuscitation details, duration of invasive mechanical ventilation, duration of non-invasive respiratory support (non-invasive mechanical ventilation, continuous positive airway pressure), duration of oxygen treatment, home O₂ requirement, BPD incidence and severity along with pulmonary complications will be collected. Standard BPD definition of mild (oxygen use for 28 days), moderate (oxygen need at 36 weeks), or severe (ventilatory support at 36 weeks), along with physiologic BPD testing at 36 weeks will be used to define BPD. This data will also be used prospectively in a future randomized control trial if feasibility study is successful. The research team members and DSMB will have access to the full data set.

DATA ANALYSIS

As the study is designed as a pilot, no formal tests of hypotheses will be conducted^{xxiii}. In Phase I, our goal is to attain skill and competency with using the device, as well as to establish that our measures are reliable and valid. Descriptive statistics will be use to assess the feasibility of measuring TV in the DR. Feasible will be defined as being able to successfully measure the TV in 80% of the infants within 60 seconds of starting PPV via the endotracheal tube.

For Phase II of the pilot project, data analysis will be limited to point estimates (e.g., means and proportions). We will describe the feasibility of using VTV in the DR, and data analysis will be limited to estimating the point estimates (e.g., means and proportions) and variability of ventilatory measures in each group and overall. We will also estimate recruitment and attrition rates, as well as the duration of the consenting process.

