- The DR staff including the attending neonatologists, advanced practitioners and respiratory therapists will be trained and will have ample time to feel comfortable about the flow sensor and the Respirationics device prior to starting the study. Our staff currently uses a similar flow sensor device in the NICU and thus we do not anticipate any significant issues pertaining to training.

Subject stopping rules:

- Development of pneumothorax, pneumomediastinum
- PiP requirement >30 cm H₂O pressure for more than 60s
- Persistent low saturation or bradycardia with 60 seconds of optimum VTV

Individual responsible for stopping/modifying the protocol: **[name], MD**, Interim Division Chief along with the IRB will serve as the Safety Monitor for the study. Any SAEs will be reported to the IRB within 48 hours of occurrence.

POTENTIAL PITFALLS AND ALTERNATIVES

Inability to measure small tidal volume: As the *Respironics NM3 monitor* has never been tested to measure TVs in the range of 2-3ml/breath, we potentially run the risk of inability to measure the TV in this range in the extremely low birth weight infants (<500gm). We do plan to measure the TV in a standard test lung after acquisition of the device to ensure accuracy. Alternatively, we may have use the *Dräger Babylog VN500 ventilator* with a flow sensor device to measure TV in the DR. This will be more challenging as having a ventilator in the DR, but is possible to have one stand by, only to measure the TV from its circuit.

Leak from the ETT: Presence of a large leak may pose a significant problem in clinical situations as it makes accurate estimation of TV difficult. We will strictly adhere to the NRP guidelines for endotracheal tube sizes according the patients weight and gestational age and will evaluate both inspiratory and expiratory TV for the study. In situations with a large leak (>50%), we will use the expiratory TV as the marker for delivered TV.

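### Phase II does not plan to separate failure to measure tidal volume from failure to adjust pressure, and leaves the control arm's sensor readings out of the measurability estimate

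*Combined protocol and SAP*

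**What the plan says.** The Randomization section states for Phase II that "Infants in both the arms will have a flow sensor at the ETT connected to Respironics NM3 monitor". Sample Size sets 30 infants, 15 per arm. The Intervention section hides the TV reading from control-arm providers, while VTV providers adjust PiP to bring TV into the goal range.

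Two of the Phase II Specific Aim #1 objectives concern delivery of VTV. One sets a joint criterion: "To assess the % of infants with measurable TV and successful adjustment of PiP to reach goal TV". The other is a single failure percentage, covering infants who do not succeed on VTV and have to change to PLV.

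Under Withdrawal/Termination Criteria, the intervention arm reverts to routine care on either of two conditions: "If TV cannot be measured or VTV cannot be provided within 60 seconds of initiating PPV via the ETT". For the other arm the text reads "Control Arm: No specific withdrawal/termination criteria will be required". The Subject stopping rules under Data and Safety Monitoring add further conditions, among them "Persistent low saturation or bradycardia with 60 seconds of optimum VTV".

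In Phase I, by contrast, measurement is an outcome in its own right: Data Analysis calls it feasible if TV is measured in 80% of infants within 60 seconds. No such stand-alone rate is named for Phase II. Data Analysis limits Phase II to point estimates and variability, by group and overall, with no hypothesis tests.

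**The concern.** The first objective joins two steps that can fail for different reasons: obtaining a TV reading, and using it to bring TV to goal. Control infants cannot meet the joint criterion because their providers do not see TV, so their readings add nothing to the planned feasibility figures. The second objective likewise gives one percentage, although the switch rule names two causes.

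The distinction matters in this trial. Potential Pitfalls and Alternatives says that the monitor is untested at 2 to 3 ml per breath and that a large tube leak makes TV hard to estimate. For failure to measure small volumes it names a different device as the alternative. A measurement failure thus points to the equipment, whereas a failure to reach goal TV with a good reading calls VTV itself into question. The planned percentages can come out the same in both cases, yet the pilot is meant to justify a larger trial.

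Some adverse courses after intubation can also occur under PLV. Persistent low saturation or bradycardia is one, and no Phase II objective reports how often it occurs in controls.

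**Working it through.** **1. The plan's own precision figure.** Sample Size says that "with 30 patients, the width of the 95% confidence will be about 55% as wide as the standard deviation". This reproduces as the width of the 95% interval for a standard deviation at n = 30: sqrt(29/45.72) = 0.796 and sqrt(29/16.05) = 1.344, a width of 0.548 SD. It describes a continuous measure and says nothing about the precision of the feasibility percentages.

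**2. What a joint percentage hides.** Suppose 12 of 15 VTV infants meet the joint criterion. Two very different results fit:

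- TV measured in 12/15 and PiP adjusted to goal in 12/12: a pure measurement problem.
- TV measured in 15/15 and PiP adjusted to goal in 12/15: a pure adjustment problem.

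Both are reported as 80%.

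**3. Precision of measurability, 15 against 30 infants.** The documents give no expected Phase II rate. I assume 80%, the Phase I threshold. The Wilson limits, with z = 1.96, are [p + z²/2n ± z·sqrt(p(1−p)/n + z²/4n²)] / (1 + z²/n).

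- n = 15: centre 0.928/1.256 = 0.739, half-width 0.191, interval 54.8% to 93.0%, width 38 points.
- n = 30: centre 0.864/1.128 = 0.766, half-width 0.139, interval 62.7% to 90.5%, width 28 points.

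The interval narrows by about a quarter (1 − 27.8/38.1 = 0.27). Exact intervals lead to the same conclusion: 51.9% to 95.7% against 61.4% to 92.3%. Adding the 10 Phase I infants (32/40) gives a Wilson interval of 65.2% to 89.5%.

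**4. Chance of missing a measurement problem.** If the true failure rate were 10% (assumed), the chance of seeing no failure is 0.9^15 = 0.21 with 15 infants and 0.9^30 = 0.04 with 30.

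**5. What a control-arm reference can show.** A VTV failure count of 3/15 (assumed) has an exact interval of 4% to 48%. If 20% of each arm had the event, the difference would have a 95% half-width of 1.96·sqrt(2 × 0.2 × 0.8/15) = 0.286, about 29 points. The control rate gives context; it does not give a usable comparison.

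**The case against.** The strongest reply is that this is a descriptive pilot and most of the information will be in the database anyway. TV and PiP are collected, the switch rule names its two causes, and nothing forbids reporting the joint objective as two proportions. Phase I isolates the measurement question under PLV, and a test-lung check is planned. Neither percentage has a go/no-go threshold, and the Phase II primary outcome is timing of initiation. Much of this stands, and it rules out several stronger readings that a reader might infer:

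- *The cause of failure cannot be determined.* Not supported. It could be tabulated from data already planned; the gap is that no such tabulation is specified.
- *Nothing comparable is scored in controls.* Not supported. Specific Aim #3 compares complications, including pneumothorax, between VTV and PLV, and Data and Safety Monitoring covers air leaks in all enrolled subjects. The events not yet compared are TV not read at 60 seconds and persistent low saturation or bradycardia.
- *Failure due to illness severity is charged to VTV.* Not established. No text says that a stop under the Subject stopping rules counts as failing VTV.
- *Measurability has no PLV reference.* Not quite. Phase I provides one, although it is small and not randomised: 8/10 would have an exact interval of 44% to 97%.
- *Measurability does not depend on the arm.* Unproven. VTV providers see the reading and may notice and correct a fault; control providers do not see it.

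The switch to PLV and the adjustment of PiP to goal TV have no PLV counterpart by construction, so reporting them in one arm is normal.

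**Conclusion.** The point holds as a gap in what is planned, not in what is recorded. Both VTV-delivery percentages can come only from the 15 VTV infants, sensor failure and PiP-adjustment failure are not planned to be separated, and the 15 controls' sensor readings are not used for measurability. At an assumed 80%, using all 30 infants narrows the Wilson interval from 38 to 28 points. That is a real gain but leaves a wide interval, and a control-arm reference at this size cannot establish or exclude an excess of failures. The larger benefit is interpretive: the pilot could tell an equipment problem from a problem with VTV, for which the plan itself foresees a different response. The change should be made because it costs almost nothing.

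**What to change.** In the Phase II Specific Aim #1 objectives, replace the joint percentage with two:

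- (a) the percentage of infants with TV measured within 60 seconds of starting PPV through the tube, in all 30 infants, by arm and overall, with 95% confidence intervals. Phase I infants should be at most a supplementary figure, since that phase includes the learning period.
- (b) among VTV infants with measurable TV, the percentage in whom PiP was adjusted to reach goal TV.

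Tabulate switches from VTV by cause: TV not measured, VTV not provided, other stop. Beside them, show the control-arm rates of TV not read at 60 seconds and of persistent low saturation or bradycardia, recorded in the same way in both arms and with no change in care.

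The denominator of (a) must include infants without a reading. The Informed Consent section seeks deferred consent only where TV was obtained, whereas Vulnerable Population requires written consent before Phase II interventions. These passages must be reconciled, because the former rule, if applied to Phase II, would remove measurement failures from the rate.

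The cost is rewording the objective, specifying one extra table and recording the named control-arm events consistently. The overall rate mixes arms in which providers do and do not see TV, so the by-arm rates must always accompany it.

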As an infant transitions to extra uterine life, pulmonary compliance changes rapidly. Total pulmonary compliance is a composite of the lung and chest wall compliances. In preterm infants, the chest wall is composed primarily of cartilage rendering the chest wall highly compliant, and as a result, the neonatal lung is more prone to collapse. Preterm lungs additionally have reduced surfactant production which further decreases lung compliance. Upon initiation of positive pressure ventilation (PPV), the rapid fluid shift in the immediate newborn period can also result in swift changes in a newborn's pulmonary compliance. Provision of maternal antenatal steroids as well as surfactant replacement therapies can positively impact the preterm pulmonary outcomes. For these preterm infants, tidal volumes generated during PPV is directly proportional to the lung compliance as demonstrated by the formula:

$$C_{dyn} = \frac{V_T}{PIP - PEEP}$$

where, V_T = tidal volume;

PIP=peak inspiratory pressure; and PEEP=positive end-expiratory pressure.

Hence, with PLV the exact same pressure due to rapidly changing lung compliance may lead to under-inflation or over-inflation of the lungs.

Once admitted in the NICU, providing VTV to preterm infants is standard practice in our NICU, with inter-provider preference over volume versus pressure ventilation, with no true consensus. However, in the DR the practice continues to be utilizing PLV and with our proposed study we seek to provide physiologically more appropriate VTV to the preterm infants right from the birth in the DR.

[figure not shown]
SIGNIFICANCE

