Control Arm: Infant will receive pressure regulated breaths, 40-60 breaths/min, PiP of 20-24cm of H₂O as recommended by 2017 Neonatal Resuscitation Program (NRP) guidelines. Reading of the TV will be blinded from the providers as in routine clinical situations

Intervention Arm: Infants in the intervention arm will receive VTV following intubation. Peak inspiratory pressure (PiP) provided via T-piece resuscitator will be visible to the providers, and the provider can regulate the PiP to achieve the desired TV goal (4-6 ml/kg), at a rate of 40-60 breaths/min according to a predefined protocol

The infants will continue to receive respiratory support as assigned by the study arm for the first 48 hours of life, following which they will receive routine VTV and weaning as per standard of care NICU practice.

BLINDING

Phase I: Providers will be blinded from the measured TV during the resuscitation.

Phase II: Due to the providers being aware of ventilation process and the need for change in ventilator settings based on the infant's TV, blood gas, blinding the providers will not be possible. Acknowledging this, we will be blinding the outcome assessment. The individual collecting the data for the two groups and performing the physiologic BPD testing will be blinded on the infant's randomization status. Need for discharge home on oxygen will be assessed by a physician not associated with the study and strict guidelines will be followed for discharge home on oxygen. Provider performing long term outcome assessment will also be blinded from the infant randomization status during the study.

PRIMARY OUTCOME VARIABLE

Phase I: Successful measurement of tidal volume in within 60 seconds of intubation and initiation of PPV.

Phase II: Timing of initiation of VTV will be similar to PLV.

STUDY ENDPOINTS

The study patient will continue in the randomized arm for the first 48 hours of life with ongoing data collection for the first 48 hours after initial neonatal resuscitation. After the first 48 hours, infant will continue standard of care per the NICU providers, with continued data collection for longer term outcomes.

SAMPLE SIZE

Phase I: We will select a convenience sample of 10 successive patients for the initial phase of the study.

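### Controls are assigned PLV for 48 hours, into the NICU stay, but the control-arm withdrawal and risk text fits only the delivery room, and no rule gives controls a mode to move to

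*Combined protocol and SAP*

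**What the plan says.** **Assignment.** The Intervention section of the protocol states that "The infants will continue to receive respiratory support as assigned by the study arm for the first 48 hours of life". It places routine VTV only after that period. Study Endpoints repeats the duration: "The study patient will continue in the randomized arm for the first 48 hours of life". It then refers to standard care by the NICU providers without naming a mode. Phase II Aim 2 plans to compare airway pressures and oxygen between the arms over the same 48 hours.

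**Usual NICU care.** Current Standard of Care Practice says that "providing VTV to preterm infants is standard practice in our NICU, with inter-provider preference over volume versus pressure ventilation, with no true consensus". Risk Benefit Assessment says: "Providing VTV to the VLBW infants is a standard of care practice upon admission to the NICU".

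**Control-arm withdrawal.** Withdrawal/Termination Criteria sets no specific criteria for Phase II controls, on the ground that "these infant will continue to receive routine care per NRP recommendations without any study related intervention".

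**Control-arm risk.** Risk Benefit Assessment says that controls face neither direct risk nor direct benefit. It names the flow sensor's dead space, under 1 ml, as the sole concern. Vulnerable Population calls the control arm minimal risk because its care is standard.

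**Exit rules.** Data and Safety Monitoring lists three subject stopping rules: air leak (pneumothorax or pneumomediastinum); PiP above 30 cm H₂O for more than 60 seconds; and persistent desaturation or bradycardia on optimal VTV.

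**The concern.** The withdrawal and risk text rests on resuscitation guidance, which describes the delivery room. The assignment lasts longer than that. Once a control infant reaches the NICU, a randomized allocation fixes the ventilation mode that a clinician would otherwise choose, and that is a study-related intervention.

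The protocol's own evidence makes this relevant to risk. The Significance section cites a meta-analysis reporting less death or BPD and fewer pneumothoraces with VTV modes than with PLV modes. If the sponsor accepts that evidence, continued PLV carries a possible risk that the risk section does not state.

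The practical stake is at the bedside. If a control infant on assigned PLV in the NICU has persistent desaturation or bradycardia, the written stopping rule does not fit, and nothing says whether a move to VTV is allowed. Clinicians may then act differently from one another. Because ventilation mode is not a listed data item, the 48-hour comparison may not show who changed.

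**Working it through.** No figure in the plan needs to be reproduced. The check sets the statements side by side.

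**1. Does the assignment reach the NICU?** Yes. The Intervention section gives 48 hours and places routine VTV after it. Study Endpoints repeats the 48 hours, and Aim 2 plans a 48-hour comparison of the arms. Together these make the duration look intended. Only the Intervention sentence names VTV as what follows.

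**2. Does the control-arm text fit that period?**

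| Statement about controls | Delivery room | NICU, to 48 h |
|---|---|---|
| No withdrawal criteria, because nothing study-related is done | Reasonable: PLV is current practice | Wrong: mode is fixed by allocation |
| Dead space is the sole concern | Reasonable | Wrong: assigned PLV is omitted |
| Minimal risk, because care is standard | Reasonable | Incomplete: PLV is within local practice, but the assignment is not mentioned |

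**3. Which stopping rules reach controls?**

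| Rule | Arm named? | Applies to a control on PLV? | Destination mode named? |
|---|---|---|---|
| Air leak | No | Yes on its wording, against the control-arm exemption | No |
| PiP above 30 cm H₂O for over 60 s | No | Yes on its wording, against the same exemption | No |
| Desaturation or bradycardia | No, but worded for VTV | Not as written | No |

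**4. Where do the written switches lead?** Withdrawal/Termination Criteria says of an intervention infant in whom tidal volume cannot be measured or VTV provided in time that "the infant will be automatically switched to receiving routine care as recommended by the NRP". Phase II Aim 1 counts infants who "fail VTV and need to be switched to conventional PLV". Data and Safety Monitoring keeps infants whose tidal volume cannot be measured on conventional PLV. All three lead to PLV or resuscitation-guideline care, which controls already receive.

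**5. How many infants?** At most the 15 controls of 30 planned (Sample Size). Only those still ventilated after transfer are exposed.

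**6. What would an exit rule cost the 48-hour contrast?** Assume that every infant has the same VTV-versus-PLV effect, and that a control who switches does so at the outset and then behaves like a VTV infant. With k switches among 15 controls, analysed as randomized, the share of the contrast retained is 1 − k/15:

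- k = 1: 1 − 1/15 = 0.933 (a loss of 6.7%)
- k = 3: 1 − 3/15 = 0.800
- k = 5: 1 − 5/15 = 0.667

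Under the same equal-effect assumption, a later switch loses less.

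**The case against.** The best defence is that PLV is not outside local practice: the protocol reports provider preference and no settled agreement, so calling control care standard is defensible. This stands. A reader might infer that controls are denied standard care, and the documents do not support that. What they show is that allocation replaces the clinician's choice and that the risk text does not say so.

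Second, the air-leak and PiP rules name no arm, safety monitoring covers all enrolled subjects, and a Safety Monitor can stop or modify the protocol. This also stands. A reader might infer that a control with a pneumothorax has no exit. On plain wording that rule applies, although it conflicts with the control-arm exemption and names no destination. The intervention-arm PiP cap does not show that controls are unprotected, because control PiP is already specified at 20-24 cm H₂O. The clear gap is desaturation or bradycardia.

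Third, a reader might infer that nearly all assigned PLV time falls in the NICU. The documents give neither time to transfer nor duration of ventilation, and early extubation is possible, so no share of time can be stated.

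Fourth, Phase II Hypothesis 3 attributes long-term outcomes to VTV in the delivery room. A reader might infer that results would be misattributed. However, Aim 3 and the later restatement of the secondary hypotheses carry no such limit, and Anticipated Results and Impact mentions continuation in the NICU. The slip is one phrase.

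Finally, the cited meta-analysis cannot be examined here, and nothing shows that its effect applies to a 48-hour period. It supports disclosing a possible risk, but not an estimate of its size.

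**Conclusion.** The point holds as an inconsistency within the protocol that should be corrected. The 48-hour assignment contradicts the reason given for having no control withdrawal criteria, and the statement that dead space is the sole concern, for the part of the 48 hours spent in the NICU. The stopping rules are unclear for controls: two can be read as applying despite the exemption, one does not fit, and none says which mode comes next.

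Up to 15 of 30 infants are affected. The number still ventilated in the NICU, their time on assigned PLV and any clinical effect cannot be estimated from the documents. The primary outcome (timing of VTV initiation relative to PLV), delivery-room measurements and sample size are unaffected, and no hypothesis is formally tested. The 48-hour contrasts and the effect sizes meant for the later trial are affected to the extent that controls change mode unrecorded.

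This rests on reading the 48-hour text as binding on mode. If the sponsor intended clinician choice after NICU admission, the Intervention section should say so.

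**What to change.** 1. **Withdrawal and stopping rules.** Replace the control-arm text in Withdrawal/Termination Criteria. State under the subject stopping rules that all three apply to controls through 48 hours, with the third reworded so that it does not depend on mode, and with release to the clinician's chosen mode, including VTV. Alternatively, state in Intervention that controls follow clinician choice after NICU admission.
2. **Risk text.** Correct Risk Benefit Assessment and Vulnerable Population to state the 48-hour mode assignment and its possible risk.
3. **Data.** Add actual ventilation mode over the 48 hours, in both arms, to Data Collection and Storage, and report crossovers beside the 48-hour contrasts and effect sizes. Mode may be recoverable from the medical record, but a planned field is safer.
4. **Minor edit.** In Phase II Hypothesis 3, remove the phrase limiting VTV to the delivery room.

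The cost is a few sentences and one recorded variable. Some controls would leave PLV early, which slightly dilutes the 48-hour contrast: by at most 6.7% per switching infant under the assumptions in the working. Making clinician choice the rule after admission could dilute it more, because more controls may then receive VTV. Sample size and primary outcome do not change.
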